We propose research to establish efficacy and sustainability of a community-social network outreach model that partners infectious disease health providers with community based organizations to successfully implement (reach, uptake, delivery and sustainment) COVID-19 rapid POS testing among a highly vulnerable and often underserved population, those who use opioids and other substances. Two distinct social network recruitment strategies, found efficacious for identifying HIV+/high risk populations and increasing uptake of HIV testing (cites) will be adapted and compared. Guided by the EPIS framework, SCT, and Andersen's model, this 2-year study will comprise three phases. In Phase 1: Adaptation of outreach recruitment strategies, we will work with our project CAB, via a CBPR approach, to adapt chain-referral and credible messenger strategies for uptake of COVID-19 testing, to finalize recruitment and on-site testing protocols, and to train the CAB in the new protocols and in continuous quality improvement strategies (Aim 1). In Phase 2: Strategy Efficacy Trial and Implementation Evaluation, we will compare the two strategies in a cross-over design at two CBOs, with initial strategy assignment randomly determined and rolled out for 4 months before the cross-over occurs. The comparison of chain-referral and credible messenger strategies is not to identify the statistical superiority of one sampling strategy in providing population estimates over the other, but instead to identify the ability of each recruitment strategy to reach the target population and increase uptake of COVID-19 tests. We will examine the impact of each strategy on (i) reach (recruitment of target population), (ii) COVID-19 testing/repeat testing, and (iii) service delivery (i.e. quarantine, medical care and contact tracing) among those who test positive for COVID-19 (exploratory) (Aim 2). In Phase 3: Sustainment, CBOs will implement the strategy proven efficacious based on outcomes, and we will examine their sustainment of the program (Aim 2). Implementation evaluation will identify participant-, staff-, and organizational-level factors that influence the feasibility, acceptability, and sustainability of each strategy in these CBOs. Participants will be assessed just prior to receipt of testing. Argus and Alliance staff will be assessed before and after the roll-out of strategies (Aim 3).

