Healthix (MIS) data: In Phase 2, participants will be asked to provide informed consent for disclosure of their HIPAA-protected health information (PHI) that is stored in Healthix, the large public NYC based health information exchange (HIE). Participant data drawn from Healthix will include prior and future (12m after end of Phase 2) COVID-19 test dates, location of testing, and results. This will improve our understanding of the potential unique reach of our underserved population recruitment strategy, the frequency and temporality of repeat testing, and the future impact of any project derived mitigation strategies to reduce barriers to appropriate testing in SUD populations. The inclusion of serologic test results also holds the potential of facilitating future COVID-19 vaccine initiatives, including the identification of high-risk members of the cohort without evidence of serologic immunity - if such immunity is found to be a reliable predictor of future risk.

Potential risks and risk related to the generalized global pandemic of COVID-19:

The physical risks of study participation are minimal as the biologic material that will be collected is limited to a one-time self collection of anterior nasal samples by us of nasal swabs. There is an additional minimal risk of exposure to SARS-CoV-2 associated with study participants proximity to another individual during recruitment activities and during testing, though this minimal risk will be mitigated by the use of appropriate PPE. To the extent possible, this research will be conducted in-person in coordination with in-person visits to Alliance and Argus for clinical and other related services (eg housing, vocational support) that are otherwise necessary. It will therefore involve a minimal additional risk of exposure to SARS-CoV-2 that is equivalent to the risk associated with any additional social contact between any two individuals.

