4.1. Brief Summary

We propose research to establish efficacy and sustainability of a community-social network outreach model that partners infectious disease health providers with community based organizations to successfully implement (reach, uptake, delivery and sustainment) COVID-19 point of service, rapid-testing among a highly vulnerable

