
4.2. Sample Size Determination

Power calculations assume that we will be able to recruit 500 participants in total (250 recruited in each strategy) for this supplement study over Phases 2a and 2b. We also assume alpha (type I error rate) of 0.05. Our primary outcome of interest is testing occurrence. Based on zip-code level testing data, the average baseline testing in the communities of interest (i.e., northern Manhattan, the Bronx) is 7842.2/100,000. If we assume that one of the methods of recruitment will have a testing rate similar to this baseline average, we will have > 80% power to detect an approximately 8 percentage point difference in testing among the recruitment strategies (7.8% vs. 16.1%) corresponding to an odds ratio of 2.27, a moderate effect size.

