4.5 Statistical Analyses

4.5.1 Analysis overview and main outcomes. The primary outcome of interest comparing the strategies will be testing occurrence (yes vs. no) as an indicator of testing uptake. An important secondary outcome will be reach measured through the number of coupons redeemed. Prior to the main analysis, all variables will be examined for distribution and outliers. Continuous outcomes will be described through means and standard deviations, while dichotomous and categorical outcomes will be described through proportions.

4.5.2 Statistical analysis for Aim 2. Models that compare the effect of recruitment strategy on outcomes related to reach, testing uptake, and service delivery will adjust for measures assessed at baseline (e.g., baseline substance use, testing history). For our primary (dichotomous) outcome (testing uptake) logistic regression will be used: $\text{logit}(\text{pi}) = \beta_0 + \beta_{\text{RecStr}}(\text{Recruitment Strategy})_{ii} + \beta_{\text{Site}}(\text{Site})_{ii} + \beta_{\text{SubUse}}(\text{Substance Use})_{ii} + \beta_{\text{TestHis}}(\text{Testing History})$, thus be β_{RecStr} which will estimate the differential effect of chain-referral vs. POL recruitment on testing uptake. The model will be adapted for secondary outcomes. Sensitivity analyses will stratify the analyses by time to determine if recruitment strategy effects differed before and after the cross-over. Demographic characteristics and other variables related to the Andersen, SCT, and EPIS models will be examined as potential mediators/moderators.

4.5.3 Statistical analysis for Aim 3. Implementation features related to acceptability, sustainability, feasibility, and fidelity will be assessed at both the staff- and individual-level. As an illustrative example, we will consider whether participants endorse time constraints and the association with testing uptake. The logistic model will take the form $\text{logit}(\text{pi}) = \beta_0 + \beta_{\text{RecStr}}(\text{Recruitment Strategy})_{ii} + \beta_{\text{Site}}(\text{Site})_{ii} + \beta_{\text{TimeCon}}(\text{Time Constraint})_{ii}$ where pi is the probability of being tested post-recruitment for the i^{th} individual. This model assesses the effect of a time barrier on the likelihood of getting testing while controlling for the differing recruitment strategies and sites.

4.6. Subject participation duration:

N/A

4.7. FDA regulated intervention:

No

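### The only strategy test compares two active outreach strategies, so it supports a relative conclusion but not the plan's claims that the outreach model, or either strategy, is efficacious

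*Combined protocol and SAP*

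**What the plan says.** The plan makes two kinds of claim.

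**Absolute claims**
- Section 4.1, in words also used in 3.1.1(a): "We propose research to establish efficacy and sustainability of a community-social network outreach model".
- Section 3.1.1(a), Justification for Intervention: the comparison is meant to "identify the ability of each recruitment strategy to reach the target population and increase uptake of COVID-19 tests".
- The Phase 3 descriptions in 3.1.1(a) and 4.1: the community organisations will implement whichever strategy has been proven efficacious.
- Section 4.8: the efficacious strategy is to be scaled up across similar organisations in New York City.
- Section 3.1.1(b), Healthix data: later test records will help in understanding "the future impact of any project derived mitigation strategies to reduce barriers to appropriate testing in SUD populations". The Study Rationale and 4.4.1 speak of long-term influence on testing.

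**Comparative claims**
- The study title, Aim 2 in 2.1.2, the close of the first paragraph of Justification for Intervention, and 3.1.4 all ask how the two strategies compare.
- The hypothesis in 4.4.1 is that chain referral does better than credible messenger.

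**The test.** Section 4.5.2 fits a logistic model for being tested, with terms for strategy, site, substance use and testing history. The strategy coefficient is the one "which will estimate the differential effect of chain-referral vs. POL recruitment on testing uptake".

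**The concern.** Words such as increase, each and efficacious need a reference condition. The null hypothesis of the planned test is that the two strategies are equal, not that a strategy adds nothing.

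At stake is what may be concluded and acted on. Phase 3 and the dissemination plan attach sustainment and city-wide scale-up to a finding of efficacy, but the data can show only which strategy did better. If the two come out alike, readers may take that as evidence against outreach in general, or as confirmation that both work. Neither reading would be supported.

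**Working it through.** **1. Is there a reference in the design?** Under Randomization in 3.1.1(a), chain referral starts at one of the two sites by 50:50 assignment and later switches to the other. Justification for Intervention describes a cross-over of the two strategies. No site or period without active outreach is designated as a reference.

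**2. Is there a reference in the analysis?** Two candidates appear, and neither is used as one.
- The area testing rate in 4.2 (7842.2/100,000, or 7.84%) serves only as the assumed rate for one of the two active strategies. It enters no model.
- Healthix prior testing is to supplement the comparison, and testing history is a covariate in 4.5.2. No model compares testing with that baseline.

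**3. The plan's own power figure.** Inputs from 4.2: 250 per strategy, 7.8% vs 16.1%, alpha 0.05. Sidedness is not stated; two-sided is assumed.
- Odds ratio = (0.161/0.839) / (0.078/0.922) = 2.27, as stated.
- Mean rate = 0.1195. SE under the null = √(2 × 0.1195 × 0.8805 / 250) = 0.0290.
- SE under the alternative = √((0.078 × 0.922 + 0.161 × 0.839) / 250) = 0.0288.
- z = (0.083 − 1.96 × 0.0290) / 0.0288 ≈ 0.91, giving power of 81.8%.

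The stated power above 80% is reproduced. It is power for a difference between strategies.

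**4. What the difference can and cannot distinguish.** Take the plan's two rates as illustrations, 250 per strategy. The 95% half-width for a difference between equal rates is 1.96 × √(2p(1−p)/250).
- Both at 16.1%: expected difference 0, half-width 1.96 × √(2 × 0.161 × 0.839 / 250) = 6.4 points.
- Both at 7.8%: expected difference 0, half-width 1.96 × √(2 × 0.078 × 0.922 / 250) = 4.7 points.

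Both intervals centre on zero, so the test result carries no information about the common level of testing.

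**5. What per-strategy estimates add.** The half-width for one proportion is 1.96 × √(p(1−p)/250).
- At 16.1%: 4.6 points, about 11.5% to 20.7%.
- At 7.8%: 3.3 points, about 4.5% to 11.1%.

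These show the level that each strategy reached, which the coefficient hides. They still do not say what would have happened without outreach.

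All figures assume independent participants, as the calculation in 4.2 does.

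**The case against.** The strongest reply is that this is a comparative trial and says so. The title, Aim 2, 3.1.4 and the 4.4.1 hypothesis all match the test. The sentence in 3.1.1(a) about each strategy has the comparison as its subject, and what it disclaims is superiority in giving population estimates. Comparing two active strategies is a reasonable choice when both are presented as efficacious for HIV testing. Section 4.5.1 already plans to describe dichotomous outcomes by proportions, and no before-after Healthix test is specified.

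All of that stands, and it limits the point to the absolute wording and what hangs on it. It does not remove the point. Section 3.1.1(a) calls success for COVID-19 testing highly plausible on the HIV evidence, and the study is proposed to establish it.

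Some stronger readings are tempting, but the documents do not support them:
- A reader might infer that the test lacks power because it rejects only about 5% of the time when both strategies work equally well. That is the type I error under a true comparative null (4.2: "We also assume alpha (type I error rate) of 0.05"), and any superiority comparison of two active arms shares it.
- A reader might infer that the test answers none of the trial's questions. It answers the comparative one.
- A reader might fear that a strategy which depresses testing below the area rate could be declared efficacious. Nothing in the documents suggests such rates, and 2.5 and 3.1.1(b) have participants tested, or offered a test, straight after the assessment.
- A reader might propose testing against the area rate, or scaling Healthix changes by it. Section 4.2 gives that rate no time window, it describes whole communities, and scaling would not remove the selection of people who came forward.

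**Conclusion.** Wrong as written, in the claims rather than in the comparison. The design and the 4.5.2 test support the statement that one strategy yielded more testing than the other. They cannot support the statements that the outreach model is efficacious, that each strategy increases uptake, or that the strategy carried into Phase 3 has been proven efficacious. A null result cannot separate both working from neither working, and a rejection shows only relative performance.

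No bias or loss of power is claimed, and the power in 4.2 is reproduced (81.8%, two-sided). The conclusion rests on the absence of any reference site, period or comparator analysis and does not depend on particular rates; the 7.8% and 16.1% above are illustrations. For Healthix the gap is loosely worded aims with no specified analysis, not a planned confounded estimate.

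**What to change.** 1. **Limit the conclusion.** In 3.1.1(a) (the Phase 3 description and Justification for Intervention), 4.1 and 4.8, state the permitted conclusion as which of the two strategies yields more reach and testing. Replace *proven efficacious* and *efficacious* with *better-performing*. Add one sentence saying that the trial cannot show an increase over no outreach.
2. **Report levels as well as the contrast.** In 4.5.1, give each strategy's number reached and proportion tested with 95% confidence intervals, whatever the between-strategy p-value. Only the intervals are new for the proportions.
3. **Bound the Healthix inference.** In the Study Rationale, 3.1.1(b) and 4.4.1, make the between-strategy difference the only inferential result for later testing. Label any before-after change descriptive, because it also contains the calendar trend and the selection of people who came forward.

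No new arm is proposed: Table 1 already shows 486 enrolled against a target of 500. The changes need no new participants, visits or data. Their cost is redrafting, a few extra estimates and a more modest claim.

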2.5. Recruitment and Retention

Recruitment of agency staff and credible messengers for staff surveys and focus groups. All agency staff will be invited to participate in the staff surveys; those staff and credible messengers directly involved in the recruitment strategies and on-site COVID-19 test delivery, either via educating testing participants and supervising credible messengers (staff) or recruiting peers in the community (credible messengers) will be invited to participate in the staff surveys and focus groups in the same way. The PI/PD will present the study to agency staff both in-person at a staff meeting and via email and interested staff will be asked to contact the research team. An email from the PI (with an attached information sheet) explaining the project and staff participation in the survey and focus group will be sent to agency leadership who will then distribute it to staff and Credible Messengers. These methods have been used successfully in our prior work with probation offices and treatment staff. The email will instruct interested staff to contact research staff directly to ask questions. For those interested in participating in focus groups, efforts will be made to schedule interviews at times that do not interfere with staff roles (e.g. lunch breaks; staff meetings). Considerable effort will be taken to ensure that staff do not feel coerced to participate. It will be emphasized to staff that participation (Y/N) is voluntary and will in no way affect their employment status. These procedures have been successfully used in PIs prior work recruiting justice and treatment staff. Retention and engagement activities will include small thank you gifts for participation in surveys, one at baseline and the other after study activities have been completed. We are unable to address staff-turnover which may impact on study retention.

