Staff, credible messenger and CAB member focus group. At the end of Phase 2, interested agency staff, credible messengers and CAB members will be invited to participate in two focus groups to understand staff attitudes and perspectives on integration of each recruitment strategy and COVID-19 testing and related services into ongoing agency workflow; changes in job role, performance, or load. Staff focus groups will be run separately from CM/CAB member group and will be conducted in a private room at the home agency. The focus groups will each take approximately 1 hour to complete. Focus groups will be digitally recorded and transcribed, with the participants' consent, to facilitate the coding and analysis of these data.

Process measures: During Phase 2, participants recruited via chain-referral or credible messengers will complete a process measure, created for the study, consisting of a brief set of questions to monitor for potential ethical concerns arising among participants during the recruitment process. These questions will be defined during the intervention development process in Phase 1 and will address issues related to any unwanted disclosure of sensitive information, perceived or actual coercion or other potential psychological harms. Staff and CMs will complete a series of checklists capturing fidelity and feasibility of either recruitment method and delivery of the on-site testing.

Biological samples: During Phase 2 participants recruited via chain-referral or credible messenger will be asked to provide biological samples for COVID-19 testing, namely anterior nasal swabs for the BD Veritor™ SARS CoV 2 and Cepheid Xpert SARS CoV 2 testing platforms. Further details of the testing process can be found in Section 3.3 Testing Capacity.

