- 3) Some participants may be engaged in treatment for substance use disorders or otherwise attempting to abstain from substance use (i.e. in recovery) at the time they engage in peer-recruitment. During the study, participants will be asked to focus recruitment on individuals they believe to be actively using substances. Therefore, it is possible that participants in recovery will have contact with peers who are actively using substances, which they would not otherwise have. Such contact may cause participants to experience cravings to return to active use.
- 4) Participants may reveal sensitive information about individuals who have not consented to participate in the study in one of two ways: a) while completing social network inventories, participants will be asked sensitive questions about their social network contacts who, in most cases, will not themselves be enrolled in the study; and b) during peer-recruitment, participants may ask social contacts about their substance use behavior, treatment access and COVID-19 risk and testing behaviors.
- 5) Staff and credible messenger participants will be asked to complete questionnaires about their organization's mission, structure, culture/climate, resources. Participants will not be asked questions that would put them at risk of criminal or civil liability or damage to financial standing, employability or reputation. Some organizational culture and climate questions, although not structured or intended to do so, could invite negative opinions critical of leaders, supervisors and/or coworkers and the risk of accidental disclosure of their responses may create discomfort for respondents or may increase the risk of repercussions to participants from supervisory staff who may be present in the focus group. In addition to being asked to complete surveys and/or to be interviewed, the work-related interactions of staff participants may be observed and other data related to quality assurance (e.g. activities that occur within Interagency work group meetings) will be collected.

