3.1.2 ADEQUACY OF PROTECTION AGAINST RISKS

3.1.2(a) Recruitment and Informed Consent

Staff, Credible Messenger and CAB recruitment

Staff will be eligible if they are currently employed at either Argus or Alliance, including Credible Messengers and CAB members. PI/PD will present the study to agency staff both in-person at a staff meeting and via email and interested staff will be asked to contact the research team. An email from the PI (with an attached information sheet) explaining the project and staff participation in the survey and focus group will be sent to agency leadership who will then distribute it to staff, Credible Messengers and CAB members. These methods have been used successfully in our prior work with probation offices and treatment staff. The email will instruct interested staff to contact research staff directly to ask questions. For those interested in participating in focus groups, efforts will be made to schedule interviews at times that do not interfere with staff roles (e.g. lunch breaks; staff meetings). Considerable effort will be taken to ensure that staff do not feel coerced to participate. It will be emphasized to staff that participation (Y/N) is voluntary and will in no way affect their employment status. These procedures have been successfully used in PIs prior work recruiting justice and treatment staff.

Staff, CAB and Credible Messenger consent

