3.3.3.1. Protocols for preventing/mitigating specific risks. Participant distress will be managed by supervising clinical staff at either Argus or Alliance. Should additional assistance be required, supervising clinical personal within either agencies will contact the PI [name], a licensed clinical psychologist, who will provide further assistance. Risks associated with breaches of confidentiality and resulting retribution due to staff responses are a concern. Breaches of confidentiality are unlikely, given the PI's commitment to and experience in maintaining participant confidentiality. Breaches are not anticipated at NYSPI/CUMC offices, because as a research facility, standards for maintaining participant confidentiality have been rigorously maintained since we began research. Breaches might nonetheless occur. During the informed consent process, participants will be told of the confidentiality procedures that are in place, but will be informed that a breach is still possible, however rare, despite these procedures. Should a breach occur, four steps will be taken. First, the participant will be informed as to the nature of the breach, and its possible ramifications. Second, the PI will immediately notify the NIDA Project Officer and the IRB. Third, the PI will review existing confidentiality safeguards to determine why and how the breach occurred (outlined below). Fourth, the PI will halt data collection until such time that the IRB can review existing procedures as to their quality and completeness. The following steps are in place to guard against breaches of confidentiality and to protect confidentiality of research data:

- 1) Provisions in all protocols will be made to ensure that a) all participants review IRB approved consent (information) forms, b) all surveys are conducted on-line via secure login and data held on a secure server or conducted via pen/paper at the participants choice of location and pace , c) no personal identifying information is collected on data forms, d) all administrative data collected are stripped of identifying information, e) no public data files contain any HIPPA identifiers, f) participants understand the voluntary nature of study participation, g) all data collected are kept in a secured, locked area with access by only certified research staff, and h) all approvals and documentation from the IRB and other approval entities are easily accessible by the PIs and research coordinators.

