- 2) All staff in focus groups, or any study related meetings, will be asked will be asked to respect the confidentiality and privacy of the other participants
- 3) The research data will be collected electronically (Healthix, participant survey data, recording of coupons). Only trained researchers will be involved in data extraction efforts and delivery of survey forms to study sites. All project staff are required to obtain the NIH web-based certification for protection of human subjects and to sign statements of confidentiality. All staff will be aware of the NYSPI/CUMC confidentiality agreements, the NIH Confidentiality Certificate, and their responsibilities regarding the Certificate's special protections. Staff members that leave the project will be reminded of their continuing obligations to maintain confidentiality. The team has internal procedures to ensure that all staff are aware of federal and state statutes and regulations regarding confidentiality of data.
- 4) Completed surveys will be downloaded from the web to a secure drive or hand delivered or mailed securely to NYSPI/CUMC offices. Research questionnaires will be coded with a unique number only. The unique ID number will appear on all records in lieu of personal names or other identifying information. Separate follow-up locator forms with identifying information will be digitally stored on password protected servers at NYSPI/CUMC offices. Unique file numbers linking questionnaires with locator forms and identifiers will be stored on the PIs computer in a password protected file NYSPI/CUMC servers. Data from agency records (Healthix) will be provided to the NYSPI team via secure data transfer. Any identifiable data will be removed from these data before transferring them to project files; the unique ID number associated with the individual will also be used exclusively with these data. The research team will not release any individually-identifiable data back to the agencies involved in the research.

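### The protocol names repercussions from supervisors in the staff focus group as a risk, but nothing keeps supervisors apart from the line staff they supervise

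*Combined protocol and SAP*

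**What the plan says.** The risk is stated twice. Item 5 of the potential risks in section 3.1.1(b) says that some questions to staff could draw criticism of leaders, supervisors or coworkers, and that accidental disclosure of the answers "may increase the risk of repercussions to participants from supervisory staff who may be present in the focus group". Section 3.3.3.1 adds: "Risks associated with breaches of confidentiality and resulting retribution due to staff responses are a concern".

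On attendance, section 3.1.1(b) says that "interested agency staff, credible messengers and CAB members will be invited to participate in two focus groups" at the end of Phase 2. The topics are how each recruitment strategy and the testing fit into agency workflow, and changes in job role, performance or load. Eligibility in section 3.1.2(a) rests on employment: "Staff will be eligible if they are currently employed at either Argus or Alliance". Section 2.5 directs the focus-group invitation to those directly involved, including staff who supervise credible messengers.

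On separation, section 3.1.1(b) has one rule: "Staff focus groups will be run separately from CM/CAB member group and will be conducted in a private room at the home agency". On conduct in the room, step 2 of section 3.3.3.1 says that staff "will be asked to respect the confidentiality and privacy of the other participants".

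**The concern.** A protocol that identifies a specific harm to participants should either remove its source or say how the harm will be contained. Here the source is the presence of a supervisor while staff discuss their work, and the design neither rules that out nor provides for it.

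Two things are at stake. The first is protection: a member of staff who criticises how a strategy was run may do so in front of the person who assesses their performance. The second is data quality: staff who foresee this may speak less freely, and the focus group is the only place where the protocol collects staff views on feasibility and acceptability in open discussion. Aim 3 depends on such views, and Table 5 lists feasibility and acceptability among the outcomes.

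**Working it through.** No arithmetic applies; the point rests on no sample size, rate or error level. The check sets the risk beside each provision that might answer it.

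**1. Can a supervisor attend?** Item 5 foresees it. Eligibility is by employment, and the invitation goes to interested staff without regard to rank. No section plans or requires a supervisor's attendance, and none prevents it.

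**2. Does the list of specific measures answer the risk?** The potential risks open with a list of six, but the discussion that follows runs to seven items. The staff risk, item 5, is the added one. The measures in section 3.1.2(b) follow the six-item list: measure 4 deals with people who have not consented, and measure 5 with breach of confidentiality. No entry corresponds to the staff risk.

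**3. Do provisions elsewhere answer it?**

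| Provision | Where | What it protects | Covers a remark heard by a supervisor? |
|---|---|---|---|
| Staff group separate from messenger and advisory-board group, private room | 3.1.1(b) | Messengers, from the staff who supervise them | Not for line staff |
| Recordings and transcripts under ID numbers | 3.1.2(b), measure 5 | The stored record | No |
| Participants told that answers are not passed to agency staff, with stated exceptions | 3.1.2(b), step 4 | What the research team passes on | No |
| No identifiable data returned to the agencies | 3.3.3.1, step 4 | The released data | No |
| Request to respect confidentiality | 3.3.3.1, step 2 | Against repetition outside the room | No; the supervisor was inside it |
| Participation voluntary, no effect on employment status | 3.1.2(a) | The decision to take part | No; it does not cover what is said |
| May stop at any time; may decline a question | 3.1.2(a); 3.1.2(b), step 4 | The person, by silence | Only by withholding the account |

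The last row matters for the data. The one protection that a line-staff member can use in the room is to say nothing, and that is how guarded accounts would arise.

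**4. Which data are touched?** Only the staff focus group. Staff views also come from the survey repeated at the end of Phase 2, which asks how palatable and useful each strategy was, and from fidelity and feasibility checklists. Neither depends on who sits in the focus group.

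**5. How many people?** The documents do not agree:

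- Section 3.1.1(a), description of Phase 2: 20 staff at each site, so 2 × 20 = 40.
- Section 3.1.1(a), agency staff paragraph: 2 staff and 8 messengers across both sites.
- Resource sharing plan: 20 staff and messengers together; if 8 are messengers, 20 − 8 = 12 staff.
- Section 4.4: 20 staff.
- Table 2: 8 staff participants.

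The stated number of staff, apart from messengers, therefore runs from 2 to 40. No section says how many supervise others in the group.

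**The case against.** The strongest reply has four parts.

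- **Item 5 is mainly about questionnaires.** Its stated mechanism is accidental disclosure of answers, which falls under breach of confidentiality and so under measure 5 of section 3.1.2(b). This is a fair reading of how the sentence begins. But the sentence ends with supervisors present in the focus group, and coding a transcript does nothing there.
- **There are protections.** A reader might infer that the protocol has no measure at all against the risk. That is not so. Section 3.3.3.1 lists safeguards after naming retribution, including a request addressed to focus-group members, and the separate groups already keep messengers apart from the staff who supervise them. What is missing is a measure for line staff and their own supervisors.
- **Bias is not shown.** A reader might infer that staff accounts are censored, or that the comparison of the two strategies is biased towards one that leadership prefers. The documents support neither. Nothing says that leadership favours a strategy, and general reticence could affect accounts of both alike. Section 4.5.3 illustrates Aim 3 with a participant-level logistic model and does not mention focus-group data. Guarded accounts are plausible, and no more than that.
- **Excluding supervisors has a price.** At the lower staff counts the group could become too small, and staff who know the workflow well would contribute only by survey. This stands as a real cost.

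**Conclusion.** The point holds in a limited form. The protocol names repercussions from supervisors in the focus group, yet has no provision that excludes them or separates them from the line staff they supervise, and its other safeguards do not reach a remark made in a supervisor's hearing. Line staff carry an avoidable employment risk, and their focus-group accounts may be guarded.

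The size cannot be quantified. It is confined to the staff focus group and leaves the testing and reach comparisons untouched. The conclusion assumes that at least one participant supervises another in the same group. The documents foresee this but do not say that it will happen; allowing attendance is inferred from the absence of an exclusion, not from a stated decision. This is a worthwhile, inexpensive improvement and not a threat to the trial's main result.

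**What to change.** In the focus-group paragraph of section 3.1.1(b), state that supervisory and leadership staff do not attend the focus group of staff they directly supervise, and that their views are taken through the end-of-Phase-2 survey, to which section 2.5 already invites all agency staff. Enter the same rule in section 3.1.2(b) as the measure answering item 5, and in the information sheet given out before the group, so that staff know it when they decide whether to take part.

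Section 2.6 gives the recruitment status as not recruiting. If the groups have already been held, report whether supervisors attended and, if they did, state it as a limitation of the staff focus-group findings.

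The cost is one sentence in each of three places, with no extra group or staff. The loss is supervisors' contribution to the discussion and possibly a small staff group. The conflicting staff numbers should be reconciled first, so that the effect of the rule on group size can be judged.
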